12 CLINICAL EFFICACY ANALYSES

The clinical efficacy analyses will be based on the ITT set, unless specified otherwise. The mITT set will be primary population for the biomarker analysis with exception of time to 50% reduction of CRP levels for which the ITT set will be primary.

12.1 Clinical Efficacy Variables

Clinical Efficacy Endpoints:

- Change from Baseline to Day 7 and Day 14 in PaO₂/FiO₂ ratio
- Time to improvement of oxygenation defined as oxygen saturation (pulse oximetry) >93% and increased by $\geq 1\%$ from Baseline breathing only room air in the 48 hours preceding the measurement during the study (Baseline to Day 28)
- Number of days without oxygen use during the study (Baseline to Day 28)

- Change from Baseline to Days 7, 14, and 28 in the score of the WHO ordinal scale
- Proportion (%) of patients with clinical improvement defined as a reduction of 2 points in the WHO ordinal scale during the study (Baseline to Day 28)
- Number of days hospitalized during the study (Baseline to Day 28)
- Proportion (%) of patients free of respiratory failure during the study (Baseline to Day 28)
- All-cause mortality rate during the study (Baseline to Day 28)

Inflammatory Biomarker Measures:

- Change from Baseline to Day 7 and Day 14 in plasma CRP levels
- Time and number of the patients to reach 50% reduction from Baseline in plasma CRP level during the treatment period (Baseline to Day 14)
- Change from Baseline to Day 7 and Day 14 in inflammatory biomarker levels including ferritin, lymphocytes, and neutrophil to lymphocyte ratio
- Change from Baseline to Day 7 and Day 14 in serum cytokine levels including IL-6, TNF- α , IL-1 β , IL-7, IL-8, IL-9, IL-10, total IL-18, G-CSF, and GM-CSF
- Change from Baseline to Day 7 and Day 14 in serum chemokine levels including CXCL-1, CXCL-9, CXCL-10, IP-10, MCP-1 and MIP-1 α

Biomarker Assessment for Kidney Injury:

- Change from Baseline to Day 7 and Day 14 in urine NGAL level
- Change from Baseline to Day 7 and Day 14 in urine KIM-1 level

Biomarker Assessment for CV Endothelial Cell Damage:

- Change from Baseline to Day 7 and Day 14 in serum VWF antigen level
- Change from Baseline to Day 7 and Day 14 in serum P-selectin level
- Change from Baseline to Day 7 and Day 14 in serum soluble thrombomodulin level

Biomarker Assessment for Target Engagement:

- Change from Baseline to Day 7 and Day 14 in plasma and/or PBMC pRIP1 level
- Change from Baseline to Day 7 and Day 14 in plasma and/or PBMC pMLKL level

12.2 Adjustments for Covariates

Baseline measurement of the respective dependent variable will be used as a covariate in analysis of covariance (ANCOVA) models for selected efficacy variables.

12.3 Subgroup Analysis

Subgroup analyses will be performed on the CRP levels, PaO₂/FiO₂ ratio and WHO ordinal scale to summarize the treatment effects across countries based on mITT set by repeating the analysis as described for biomarker in [Section 14.1.1 CRP Levels](#) and preliminary efficacy

endpoints in [Section 13.1.1 PaO₂/FiO₂ ratio](#) and [Section 13.1.4 WHO ordinal scale](#) by country (USA, Mexico and Pakistan).

A subgroup analysis will also be performed on the duration of hospitalization after treatment, to summarize the treatment effect on those patients who completed study treatment, by repeating the analysis as described for hospitalization in [Section 13.1.5 Days of Hospitalization](#) for the subgroup of patients that completed treatment. Completed patients are defined as those patients that indicated 'Yes' to 'Was Study Treatment Completed?' on the End of Treatment CRF.

A subgroup analysis will also be done for the derived PaO₂/FiO₂ ratio to summarize the treatment effects across countries based on mITT set, by repeating the analysis as described for biomarker in [Section 13.1.1.1](#) by country (USA, Mexico and Pakistan).

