### 6.1. Treatments Administered

Study Drug Name:	SIR1-365	Placebo
Dosage formulation:	Tablets	Matching tablets
Unit dose strength/Dosage level:	100 mg tablets	NA
Route of Administration	Oral/gastric tube	Oral/gastric tube
Dosing Instructions:	Take 1 tablet three times daily	

Food and water will be allowed as needed.

The first dose of study treatment will be administered in the hospital on Day 1 after all eligibility criteria are met and randomization procedures are completed. The time of first dose establishes time zero for subsequent doses. The exact time of study treatment administration as well as the dosage (number of tablets taken) will be recorded for all doses given while in the hospital.

If hospitalized, patients are to take study treatment according to the dosing schedule (once every 8 hours  $\pm$  1 hour from Day 1 up to Day 14). If any dose of study treatment is missed, defined as no medication intake 1 hour after the scheduled dosing time, the event should be recorded in electronic Case Report Form (eCRF) and the patient should resume dosing at the next scheduled dosing time.

If the disease worsens, the patients may require mechanical ventilation and be unable to swallow study medication. In such cases, the medication will be given as an oral suspension via nasogastric tube. The suspension will be prepared immediately before dosing by dispersing one 100-mg tablet of SRI1-365 in a container with about 20 mL of water and stirring the mixture approximately 3-5 times in about 5 minutes. The oral suspension will be administered within 1-2 minutes after the preparation. The container will then be rinsed twice with about 20 ml of water each, which will be administered to the patient as well. The details for the preparation and administration of oral disintegrated suspension will be included in Pharmacy Manual.

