## **7. Discontinuation of Treatment and Study**

### **7.1. Discontinuation of Treatment**

Study treatment for an individual patient will be up to 14 days (whether or not medication is taken) or until a treatment discontinuation criterion is met. Reasons for discontinuation of treatment include the following:

- Adverse Events
- Pregnancy
- Death
- Noncompliance resulting in protocol deviation
- Withdrawal of consent
- Investigator decision
- Other (specify)

A patient may withdraw from the study at any time at his/her own request, at the discretion of the investigator for safety, behavioral, or administrative reasons. If the patient withdraws consent for disclosure of future information, the sponsor may retain and continue to use any data collected before such a withdrawal of consent

Upon occurrence of a serious or intolerable AE where study treatment discontinuation is considered, the Investigator should confirm with the medical monitor. If a patient is discontinued because of an AE, the event will be followed until it is resolved, based on the medical judgement of the Investigator.

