11.1 Extent of Exposure

All patients are to receive 1 tablet, 3 times daily for 14 days. To fit into the clinical practice of treating patients with severe COVID-19, screening visit and baseline visit can be combined in some patients. In that case, the number of dosing could be less than 3 times on that day. Patients discharged from the hospital prior to Day 14 will not take any study drug after discharge.

The extent of exposure to study drug will be examined by assessing the total number of tablets received per patient. The total number of tablets taken per patient will be summarized using descriptive statistics by treatment group.

Additionally, the duration of treatment (days) will be calculated as follows:

- Treatment duration (days)=(Date of last administration–Date of first administration) + 1

The treatment duration per patient will be summarized using descriptive statistics by treatment group.

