13.1.5 Days of hospitalization

Days of hospitalization after treatment will be determined using the ‘Study Drug Administration’ and ‘Hospitalization Details’ eCRFs. The date and time (in format 23:59) of 1st dose of study drug and discharge will be collected.

Duration of hospitalization after treatment up through 14 days will be calculated as

- Duration of hospitalization after treatment (days) = (Date and time of discharge – Date and time of 1st dose of study drug)/60/24

Missing discharge times will be assumed to be ‘23:59’ in order to calculate the maximum duration of time hospitalized. In the event a patient is hospitalized more than 14 days, 14 days will be used for analysis.

For patients that died within the first 14 days while hospitalized, the duration of hospitalization will be imputed as 14 days in order not to underestimate the number of days of hospitalization. In the unlikely event a patient dies within 14 days but subsequent to discharge, the number of days hospitalized will be 14 minus the number of days from discharge to death.

For patients with multiple hospitalizations in the first 14 days, the sum of all intervals will be calculated for analysis.

Duration of hospitalization after treatment as a continuous variable will be summarized descriptively by treatment and analyzed using a 1-way ANOVA model with a single term for treatment.

A similar analysis will be done for the total duration of hospitalization:

- Total duration of hospitalization (days) = (Date and time of discharge – Date and time of admission)/60/24

Missing admission times will be assumed to be ‘00:00’ and missing discharge times will be assumed to be ‘23:59’ in order to calculate the maximum duration of time hospitalized.

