Appendix 5: List of Tables, Listings, and Figures

The following proposal for Sections 14 and 16.2 is completed according to ICH E3² guidelines. The heading numbers and description are in **bold**. Minor changes from this planned index do not need to be amended in the SAP.

Index of Section 14

Table Number	Table Title
14.1	Demographic Data
14.1.1.1	Patient Disposition
14.1.1.2	Analysis Sets
14.1.1.3	Patient Visits
14.1.2	Number of Patients Randomized by Site and Treatment Group
14.1.3	Screen Failures
14.1.4	Demographic and Baseline Characteristics
14.1.5.1	Prior Medications by ATC Class and Preferred Term
14.1.5.2	Concomitant Medications by ATC Class and Preferred Term
14.1.5.3	Concomitant Medications Taken for COVID-19 by ATC Class and Preferred Term
14.2	Efficacy Data
14.2.1.1.1	Change in PaO ₂ /FiO ₂ Ratio from Baseline
14.2.1.1.2	Change in PaO ₂ /FiO ₂ Ratio from Baseline at Day 7 and Day 14 (LOCF)
14.2.1.2.1	Change in PaO ₂ /FiO ₂ Ratio from Baseline by Country - Subgroup Analysis
14.2.1.2.2	Change in PaO ₂ /FiO ₂ Ratio from Baseline by Country at Day 7 and Day 14 (LOCF) - Subgroup Analysis
14.2.1.3.1	Change in PaO ₂ /FiO ₂ Ratio from Baseline - Exploratory Analysis
14.2.1.3.2	Change in PaO ₂ /FiO ₂ Ratio from Baseline at Day 7 (LOCF) and Day 14 - Exploratory Analysis
14.2.1.4	PaO ₂ /FiO ₂ Ratio at Day 7 Using MMRM Model
14.2.1.5.1	Change in Derived PaO ₂ /FiO ₂ Ratio from Baseline
14.2.1.5.2	Change in Derived PaO ₂ /FiO ₂ Ratio from Baseline by Country - Subgroup Analysis
14.2.2.1	Summary of Time to Improvement of Oxygenation
14.2.3.1	Analysis of Number of Days without Oxygen Use (Baseline to Day 14)
14.2.3.2	Analysis of Number of Days without Oxygen Use (Baseline to Day 28)
14.2.4.1.1	Change in WHO Ordinal Scale from Baseline
14.2.4.1.2	Change in WHO Ordinal Scale from Baseline at Day 7, Day 14 and Day 28 (LOCF)
14.2.4.2.1	Change in WHO Ordinal Scale from Baseline by Country - Subgroup Analysis

14.2.4.2.2	Change in WHO Ordinal Scale from Baseline by Country at Day 7, Day 14 and Day 28 (LOCF) - Subgroup Analysis
14.2.4.3	Proportion of Patients with Clinical Improvement Defined by at least 2 Points Reduction in WHO Ordinal Scale
14.2.4.4	Summary of Time to Clinical Improvement Defined by at least 2 Points Reduction in WHO Ordinal Scale
14.2.5.1	Summary of Days of Hospitalization
14.2.5.2	Summary of Days of Hospitalization for Patients who Completed Treatment – Subgroup Analysis
14.2.6	Proportion of Patients with Respiratory Failure During Study

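### The completer subgroup for hospital stay selects patients on a post-randomisation event tied to the endpoint, so its between-arm test is not a randomised treatment effect

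*SAP*

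**What the plan says.** SAP 12.3 adds a subgroup analysis of the duration of hospitalisation after treatment. It repeats the SAP 13.1.5 analysis in completers, and its purpose is "to summarize the treatment effect on those patients who completed study treatment". The definition reads "Completed patients are defined as those patients that indicated" yes to the completion question on the End of Treatment form. It gives no number of doses or days and no rule for early discharge. The output is Table 14.2.5.2, "Summary of Days of Hospitalization for Patients who Completed Treatment – Subgroup Analysis".

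SAP 13.1.5 measures stay from first dose to discharge and sets a ceiling: "In the event a patient is hospitalized more than 14 days, 14 days will be used for analysis". Patients who die in hospital within 14 days are also given 14 days. The model is a one-way ANOVA with treatment as its only term. SAP 8 declares significance at a two-sided p below 0.05, and Protocol 10.3 makes no adjustment for multiple endpoints.

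On dosing, SAP 11.1 says "All patients are to receive 1 tablet, 3 times daily for 14 days", and also "Patients discharged from the hospital prior to Day 14 will not take any study drug after discharge". Protocol 7.1 is looser: "Study treatment for an individual patient will be up to 14 days (whether or not medication is taken"). Protocol 6.1 sets the interval for hospitalised patients: "patients are to take study treatment according to the dosing schedule (once every 8 hours", with a one-hour tolerance).

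**The concern.** Discharge ends both the treatment and the outcome clock. Length of stay therefore largely decides how long a patient can be treated, and so may decide who is called a completer. The subgroup is formed after randomisation by something the drug may influence, yet the SAP applies an ordinary between-arm test and describes the result as a treatment effect.

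The risk is a wrong inference from one supplementary table. A null result could be read as no benefit in patients who received the whole course. A favourable result could be read as benefit in patients who actually took the drug. The design supports neither conclusion.

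**Working it through.** The plan has no figure to reproduce: 30 per group is stated not to be calculated, and no SD or effect size is given for hospital stay. The check is exact arithmetic on the possible values, followed by a simulation under stated assumptions.

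**Reading 1: completed means the full 14-day course.** Inputs are three doses a day for 14 days (SAP 11.1), 8-hourly dosing (Protocol 6.1), fewer than three doses allowed on Day 1 when screening and baseline are combined (SAP 11.1), the Day 14 ±2 window (schedule of assessments) and the 14-day cap (SAP 13.1.5).

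Time of last dose after first dose = (number of doses − 1) × 8 h. A completer's stay lies between that time, a, and 14 days. The largest possible between-arm difference in means is 14 − a, and the largest possible SD is (14 − a)/2.

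| Case | Doses | Last dose | Range (days) | Max difference | Max SD |
|---|---|---|---|---|---|
| Full Day 1, end on Day 14 | 42 | 41 × 8 = 328 h = 13.67 d | 13.67–14 | 0.33 | 0.17 |
| One dose on Day 1, end on Day 14 | 40 | 39 × 8 = 312 h = 13.0 d | 13–14 | 1.0 | 0.5 |
| Full Day 1, Day 12 counts | 36 | 35 × 8 = 280 h = 11.67 d | 11.67–14 | 2.33 | 1.17 |
| One dose on Day 1, Day 12 counts | 34 | 33 × 8 = 264 h = 11.0 d | 11–14 | 3.0 | 1.5 |

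The one-hour tolerance moves these limits by only about 0.04 day (1/24). In every row, a patient sent home before the last dose is excluded by construction.

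**Simulation set-up** (400,000 patients per arm). These assumptions are not from the documents: log-normal stay with log-SD 0.6, and in-hospital death and treatment discontinuation both more likely in sicker patients. The 14-day cap and the rule for deaths are those of SAP 13.1.5. Differences are SIR1-365 minus placebo.

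With 10% death and 5% discontinuation in both arms, and full-course completion set at 13.67 days:

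| Median stay, placebo vs SIR1-365 | All randomised | Full-course completers | Completers per 30, placebo / SIR1-365 |
|---|---|---|---|
| 8 vs 6 d | −1.54 d | −0.003 d | 4.1 / 1.7 |
| 10 vs 7 d | −1.94 d | −0.003 d | 6.9 / 2.8 |
| 12 vs 9 d | −1.52 d | −0.003 d | 9.8 / 5.5 |

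**Reading 2: completed means treated until discharge or Day 14.** Values now vary (SD about 3.5 to 3.7 days), so the analysis is not empty, but deaths and discontinuations leave the subgroup. With the same underlying stay distribution in both arms (median 8 days):

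| Death, placebo / SIR1-365 | Discontinuation, placebo / SIR1-365 | All randomised | Completers |
|---|---|---|---|
| 10% / 10% | 5% / 5% | +0.01 d | +0.01 d |
| 10% / 10% | 5% / 20% | −0.01 d | −0.34 d |
| 20% / 5% | 5% / 5% | −0.51 d | +0.36 d |
| 5% / 20% | 5% / 20% | +0.53 d | −0.58 d |

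In the last two rows the sign reverses. In the fourth, the completer comparison favours the arm with more deaths.

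A hand example shows the mechanism. Take 3 in-hospital deaths among 30 in one arm, none in the other, and a mean stay of 7 days for everyone else. The all-patient means are (27 × 7 + 3 × 14)/30 = 231/30 = 7.7 days against 7.0. The completer means are 7.0 against 7.0.

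**The case against.** **Circularity.** A reader might infer that the subgroup is simply circular and its result empty. That needs the full-course reading, which the documents do not settle. SAP 11.1 plans 14 days, and Protocol 3.1 and 7.2.1 speak of patients who complete the 14-day treatment. Against that, Protocol 7.1 allows up to 14 days and does not name discharge among its reasons for stopping treatment, and footnote 2 of the schedule of assessments treats early discharge as an end-of-treatment visit. The annotated eCRF may resolve this, but it is not among the documents. So strict circularity is conditional.

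**Certain bias.** Under the other reading, bias is possible rather than shown. It has no fixed size or direction and was absent in the simulation when death and discontinuation rates were equal. What stands is that randomisation does not protect the comparison.

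**Hidden harm.** A reader might infer that the table conceals deaths. The rest of the plan does not support that. The subgroup is additional. Deaths keep their 14-day value in the ITT stay analysis (Table 14.2.5.1) and appear in the mortality table (14.2.7) and the fatal adverse event table (14.3.1.11). The 0.7-day gap in the hand example would be within noise anyway: with an assumed SD of 3.5 days and 30 per arm, the standard error is 3.5 × √(2/30) = 0.90 day.

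**Table title.** Table 14.2.5.2 is not itself titled a treatment effect. That wording is in the text of SAP 12.3 only.

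**Total duration.** SAP 13.1.5 also has an admission-to-discharge duration with no stated cap. SAP 12.3 names the capped after-treatment measure, and a total-duration version would still select after randomisation.

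**Weight.** This is one supplementary table on a secondary endpoint in an exploratory, unpowered Phase 1b safety study. That argues for minor severity, not for leaving the test in place.

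**Conclusion.** Wrong as written; minor severity. SAP 12.3 applies a between-arm test, and the term treatment effect, to a group selected on a post-randomisation event tied to the endpoint.

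Under the full-course reading, nearly every value lies at about 13 to 14 days (about 11 to 14 if the Day 14 ±2 window counts). Early discharges are excluded, and assumed true effects of about −1.5 to −1.9 days shrank to −0.003 day with completion at 13.67 days. Under the until-discharge reading, the comparison may be biased in either direction whenever death or discontinuation rates differ by arm. The examples ran from −0.58 to +0.36 day with identical underlying stay.

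The ranges follow from the documents' own dosing interval and cap. The simulated sizes rest on assumed stay, death and discontinuation figures and are illustrations only. The ITT stay analysis, the mortality table and the primary safety endpoint are unaffected.

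**What to change.** Delete this subgroup from SAP 12.3 and Table 14.2.5.2 from Appendix 5. Alternatively, keep the table as descriptive only, with these changes:

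- no ANOVA, confidence interval or p-value;
- no treatment-effect wording in SAP 12.3;
- a sentence saying whether a patient discharged before Day 14 counts as having completed treatment.

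In either case, state that any inference on hospital stay rests on the ITT analysis in SAP 13.1.5.

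The cost is a few lines of SAP text and one table shell, with no new data. The protocol's own hospitalisation analysis (Protocol 10.3.1) does not ask for this subgroup, so deletion breaks no protocol commitment. Subgroups fixed at baseline are optional and not needed for this repair. A split by baseline WHO score of 4 against 5 or more could leave a very small cell: score 4 means no oxygen therapy, and eligibility requires signs of severe illness.

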12.4 Handling of Dropouts or Missing Data

In the analysis of CRP levels if more than 10% of patients in either arm has missing Day 7 CRP values, a supportive analysis will be performed using a mixed model for repeated measures (MMRM). Details of this analysis is provided in [Section 14.1 Inflammatory Biomarkers](#).

Additionally, in the analysis of the PaO₂/FiO₂ ratio if more than 10% of patients in either arm has missing Day 7 values, a supportive analysis will be performed using a mixed model for repeated measures (MMRM). Details of this analysis is provided in [Section 13.1.1 PaO₂/FiO₂ ratio](#).

For any patients with missing results on study day 7, the Day 7 results for coagulopathy, cardiac function damage, the PaO₂/FiO₂ ratio, the WHO ordinal scale and CRP levels will be imputed with the last available assessment, prior to study day 7. Similarly, Day 14 missing observations will be imputed with the last available assessment that occurred after Day 7 and prior to Day 14. Where applicable, Day 28 missing observations will be imputed with the last available assessment that occurred after Day 14. More details are given in the relevant sections of this analysis plan.

12.5 Interim Analysis and Data Monitoring

No interim analysis is planned for this study. However, during the study, unblinded safety, biomarker, and clinical efficacy data will be reviewed by an independent data monitoring committee (IDMC) approximately when roughly 20 and 40 patients are enrolled.

13 METHODS OF EFFICACY ANALYSIS

13.1 Clinical Efficacy Analyses

Although the study is not powered for hypothesis testing of secondary endpoints, P-values will be generated to aid interpretation in addition to CIs about the estimates.

For all continuous measures, exploratory comparisons between treatment groups will be tested by comparing the mean change from Baseline values between treatment groups.

13.1.1 PaO₂/FiO₂ ratio

The PaO₂/FiO₂ ratio, change and percentage change from Baseline in PaO₂/FiO₂ ratio will be summarized by visit and treatment using both simple descriptive statistics and model-based estimates. A non-parametric Wilcoxon Rank Sum test will be used to compare the treatment groups with respect to the percentage change from baseline values at Day 7 and Day 14/EOT.

A separate summary table will be produced, similar to what is described above, summarizing the results at Day 7 (assessments taking place on study day 7) and Day 14 (assessments taking place on study day 14). For any patients with missing Day 7 results, the Day 7 results will be imputed using the last value reported prior to study day 7. Similarly, Day 14 missing observations will be imputed with the last available assessment that took place after study day 7 and prior to study day 14. A summary table will be produced, summarizing these (imputed and reported) results.

The change from Baseline at each visit will be compared between treatment groups using an ANCOVA model with fixed effects for treatment and the Baseline score as a continuous covariate. Comparison of the SIR1-365 dose and placebo will be constructed based on least-squares means (LSMean) from the model.

The mean change and mean percentage change from Baseline up to Day 14, using the actual study day for Day14/EOT assessments, will be plotted per treatment group using line graphs.

As a sensitivity analysis, to assess the impact of missing data, if more than 10% of patients in either arm has a missing Day 7 PaO₂/FiO₂ ratio, a MMRM analysis will be performed. The PaO₂/FiO₂ ratio will be analyzed by a MMRM with treatment group, Day (Days 2 to 14), and treatment group-by-Day interaction as fixed factors, and the Baseline score as a continuous covariate. Day will be used as the repeated measure using an unstructured covariance structure. For both treatment groups, at Day 7, the geometric LS mean in the PaO₂/FiO₂ ratio and corresponding 95% CI will be presented. The output will also include the estimated geometric LS mean ratio for SIR1-365 dose and placebo, the corresponding 95% CI and corresponding two-sided P-value for the ratio.

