#### **8.1.1. $\text{PaO}_2/\text{FiO}_2$ ratio**

$\text{PaO}_2/\text{FiO}_2$  ratio will be evaluated by blood gas analyzer at screening for eligibility determination, within 30 minutes before dosing on Day 1 as baseline, and within 30 minutes after 2nd dose on Day 7 and Day 14. Change from baseline to Day 7 and to Day 14 on  $\text{PaO}_2/\text{FiO}_2$  ratio will be one of the secondary efficacy measures in this study.

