5 STUDY DESIGN AND PLAN

This is a multicenter, randomized, double-blinded, placebo-controlled study to evaluate safety and preliminary efficacy of SIR1-365 in patients with severe COVID-19. The primary objective is to assess the overall safety and tolerability of SIR1-365 administered orally at 100 mg, 3 times per day (TID) for 14 days relative to the placebo group. The secondary objectives are to assess the effects of SIR1-365 on clinical efficacy endpoints and the biomarkers indicative of

inflammation, target engagement, kidney injury and CV endothelial cell damage as well as SIR1-365 pharmacokinetics (PK).

Approximately 60 eligible patients will be randomly assigned at a 1:1 ratio to receive either SIRI-365 at 100 mg, TID or matching placebo for up to 14 consecutive days. For ethical and medical reasons, standard-of-care treatments for COVID-19 will be provided to all patients. Study treatments (either SIRI-365 or matching placebo) will be given as add-on therapy.

Patients could be hospitalized and treated for up to 14 days. Patients will be assessed daily while hospitalized. If the patients are discharged from the hospital before Day 14, all the assessments planned for Day 14 should be carried out before discharge. If a patient is still hospitalized after Day 14, no study drug will be administered after the last dose on Day 14.

It is preferred that the follow-up visit is in person to obtain safety laboratory tests. However, infection control or other restrictions may limit the ability of the patients to return to the clinic. In this case, the follow-up visit may be conducted by phone and only safety data will be obtained. Study drugs will not be administered for early discharged patients. Follow-up visit will be scheduled approximately on Day 28 (± 3) or 14(± 3) days after the last dose for those who are discharged from the hospital before Day 14.

Table 5.1 Treatment Administered

Study drug name:	SIR1-365		Placebo	
Dosage formulation:	Tablets		Matching tablets	
Unit dose strength/Dosage level:	100 mg tablets		NA	
Route of administration	Oral/gastric tube		Oral/gastric tube	
Dosing instructions:	Take 1 tablet three times daily			

Food and water will be allowed as needed.

Study procedures to assess safety, preliminary efficacy, biomarkers, and PK are shown in below table.

Table 5.2 Schedule of Assessments¹²

Days	Screening	Treatment in Hospital								Follow-up Visit/EOS
	-7 to -1	1 ¹	2-6	7	8-9	10	11-13	14 (± 2) /EOT ²		

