13.1.4 WHO ordinal scale

The WHO ordinal scale is a 10-level ordered categorical scale developed by a special committee at WHO to measure illness severity over time. This endpoint will be collected 4 times during the study: at Baseline and on Days 7, 14, and 28.

The scale will be used to assess patients' clinical status during the study. A 2-point reduction on the score of WHO ordinal scale is considered as clinical improvement.

When completing the WHO Ordinal Scale at Day 14/ EOT, if the patient has received physician orders to be discharged from the hospital, the score should be a 3 or less (*no longer hospitalized*).

Change and percentage change from Baseline to Days 7, 14, and 28 in the scores of WHO ordinal scale as a continuous variable will be summarized by visit and treatment.

A separate summary table will be produced, similar to what is described above, summarizing the results at Day 7 (assessments taking place on study day 7), Day 14 (assessments taking place on study day 14) and Day 28 (assessments taking place on study day 28). For any patients with missing Day 7 results, the Day 7 results will be imputed using the last value reported prior to study day 7. Similarly, Day 14 missing observations will be imputed with the last available assessment that took place after study day 7 and prior to study day 14. Day 28 missing observations will be imputed with the last available assessment that took place after study day 14. A summary table will be produced, summarizing these (imputed and reported) results.

Categorical summaries of patients having a clinical improvement during the study (Baseline to Day 28) will be generated presenting the number and percentage of patients with an improvement at any visit from Baseline to Day 28. Associated 95% CI for the proportion of improvement will be provided for each treatment group using the Clopper-Pearson method.

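### The SAP's carry-forward tables use exact study days, so Day 14 visits on Days 15–16 drop out, some missing Day 7 values become baseline, and WHO deaths are not carried forward

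*SAP*

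**What the plan says.** SAP 13.1.1 adds to the by-visit PaO2/FiO2 summary a separate table whose last column is "Day 14 (assessments taking place on study day 14"; Day 7 is likewise study day 7 exactly. The filling rules are:

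- Day 7: "the Day 7 results will be imputed using the last value reported prior to study day 7".
- Day 14: "Day 14 missing observations will be imputed with the last available assessment that took place after study day 7 and prior to study day 14".
- Where the endpoint has a Day 28 column (for example WHO, SAP 13.1.4): "Day 28 missing observations will be imputed with the last available assessment that took place after study day 14".

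SAP 12.4 states the rule generally ("Day 14 missing observations will be imputed with the last available assessment that occurred after Day 7 and prior to Day 14"). It recurs in 11.7 (coagulopathy), 11.8 (cardiac), 13.1.4 (WHO, including the second stacked-bar plot), 13.2 (repeated correlations) and 14.1.1 (CRP, including the PP set). Appendix 5 also lists LOCF versions of the country subgroup tables.

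The schedule is looser. SAP Table 5.2 sets Day 14 at ±2 days and gives no window for Day 7. SAP 5 says "Follow-up visit will be scheduled approximately on Day 28" (±3), or 14 ±3 days after the last dose for patients discharged before Day 14.

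Assessments are sparse for two endpoints. For the WHO scale, "This endpoint will be collected 4 times during the study: at Baseline and on Days 7, 14, and 28". Protocol 8.1.1 measures PaO2/FiO2 at screening, Day 1, Day 7 and Day 14, and the endpoint is "Change from baseline to Day 7 and to Day 14 on" that ratio. CRP, coagulation and cardiac tests are done on Days 1, 3, 7, 10 and 14.

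SAP 8.4 assigns early-discharge assessments to Day 14/EOT in all summaries, whatever the actual day.

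**The concern.** The LOCF outputs exist to deal with missing data. Read literally, they do three unhelpful things. They set aside a Day 14 value obtained within the permitted window. They can represent a missing Day 7 value by baseline, which pulls both arms towards no change. And on a scale where death is the worst category, they do not keep a dead patient at that category.

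Elsewhere the SAP does give death explicit treatment: as a competing risk for time to improvement (13.1.2, 13.1.4.1) and as 14 days in the hospitalization duration (13.1.5). The WHO LOCF rules have no counterpart. SAP 6 says the study's estimates are for use in planning later trials, and with 30 patients per arm a handful of misplaced values can be visible in a mean.

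**Working it through.** The documents give no effect size, SD or missing-data rate, so there is no planned figure to reproduce. The check applies the rules literally to each permitted day.

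**Day 14 column, window Days 12–16**

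| Visit on study day | Enters Day 14? |
|---|---|
| 12, 13 | yes, by carry-forward |
| 14 | yes, directly |
| 15, 16 | no |

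Three of the five permitted days reach the column and two do not. What replaces a Day 15–16 visit depends on the schedule:

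- PaO2/FiO2 and WHO: nothing is scheduled on Days 8–13, so an inpatient with no other value there is missing at Day 14.
- CRP, coagulation, cardiac: the Day 10 value is used.
- WHO, coagulation, cardiac also have a Day 28 column. A Day 15–16 value lies after study day 14, so it becomes Day 28 if nothing later exists. For WHO this is plausible, because SAP 5 says a phone follow-up yields safety data only.

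**Day 28 column.** All seven days from 25 to 31 enter, because any last assessment after study day 14 qualifies and no upper limit is set. For early discharges, take discharge (and last dose) on day d = 2 to 13 and follow-up on days d+11 to d+17. That is 12 × 7 = 84 combinations. Three fall on or before Day 14 (d = 2 with follow-up on Day 13 or 14; d = 3 with follow-up on Day 14), so 84 − 3 = 81 are usable.

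**Day 7 column**

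- CRP, coagulation, cardiac: a missing Day 7 takes Day 3.
- PaO2/FiO2 and WHO, patient still in hospital with no post-baseline value before Day 7: the last value before study day 7 is baseline, so change = 0. This includes an assessment made one day late, on Day 8. That Day 8 value then fills Day 14 only if there is no value on study day 14 and none on Days 9–13.
- Patient discharged on Days 2–6: the Day 14/EOT assessments are done at discharge, so the literal rule carries a post-baseline value to Day 7. The same value cannot fill Day 14.

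If section 8.4 governs instead, discharge values from Days 2–6 belong to Day 14/EOT and do not feed Day 7, and baseline carry-forward becomes more common. The SAP does not say which applies.

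**WHO score after death**

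| Day on which score 10 is recorded | Fills Day 7 | Fills Day 14 | Fills Day 28 |
|---|---|---|---|
| 2–7 | yes | no | no |
| 8–14 | no | yes | no |
| after 14 | no | no | yes |

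The gaps arise in the columns after the death: Days 14 and 28 in the first row, Day 28 in the second. If no score is recorded for a death before Day 7, the Day 7 column shows baseline.

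**Size, by assumption**

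- Let a share m in both arms have Day 7 change set to zero, with these patients otherwise like the rest. The expected difference is (1 − m) × δ: a factor of 0.95, 0.90, 0.80 or 0.70 for m = 5, 10, 20 or 30%.
- With 30 per arm, two-sided 0.05, an assumed standardized difference of 0.8 and constant SD, power falls from 87.3% to 83.7%, 79.6%, 69.8% and 58.3%. At 0.5 it falls from 49.1% to 45.2%, 41.4%, 34.1% and 27.3%.
- One unscored death at an assumed baseline WHO score of 5 is an error of 10 − 5 = 5 points, or 5 / 30 = 0.17 on an arm mean.

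**The case against.** The strongest reply is that these outputs are supplementary. The SAP calls them separate tables, and the by-visit tables are not limited to exact days. The primary endpoint is the proportion of patients with TEAEs, which no LOCF rule touches, and the study is exploratory and unpowered. All of this stands, and it limits the point to the LOCF tables, plots and repeated correlations.

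Other safeguards help less. The MMRM for PaO2/FiO2 and CRP runs only if more than 10% of an arm lacks Day 7 (at least 4 of 30), and WHO has no equivalent. The oximetry-derived PaO2/FiO2 ratio (13.1.1.1) has its own tables, with no LOCF version in Appendix 5.

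Day 15–16 visits may also be few. Protocol 8.1.1 ties the Day 14 PaO2/FiO2 to the second dose and no study drug is given after Day 14, so a later PaO2/FiO2 cannot meet that timing. Two of five is a count of calendar days, not of patients.

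On deaths, the scale has a score for death, and sites may enter 10 at each later scheduled visit. If they do, the columns are right. The SAP does not require it.

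A reader might infer more than the text supports:

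- That in-window visits are discarded at all three time points. Days 12–13 enter by carry-forward, Days 25–31 all enter Day 28, and Day 7 has no stated window to fall inside.
- That every missing Day 7 value becomes no change. Under the actual-day reading, patients discharged on Days 2–6 supply a post-baseline value.
- That a Day 8 value always becomes Day 14. A patient with an ordinary Day 14 assessment keeps it.

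**Conclusion.** The point holds for the LOCF outputs only, in three parts. Day 14 assessments made on Days 15–16 are lost from Day 14 and, for endpoints with a Day 28 column, can reappear there. Inpatients with no PaO2/FiO2 or WHO value on study day 7 and no earlier post-baseline value are given zero change. The literal WHO rules do not carry a death to later time points.

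The first two follow from the SAP's wording and schedule alone. The third assumes that a death score is recorded once, or not at all, rather than re-entered at later visits. How many patients are affected cannot be derived from the documents; the attenuation, power and 0.17-point figures are illustrations under stated assumptions. The documents do not support a claim that the by-visit efficacy results or the safety conclusion are compromised. It should still be corrected, because a stated rule drops or replaces observed data and the repair is small.

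**What to change.** In SAP 12.4 and the sections that repeat its rule, for the LOCF outputs:

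1. Use the observed Day 14/EOT assessment from Days 12–16 as Day 14 before any imputation, and do not reuse it as Day 28. Tie this to the visit label, so that an early-discharge follow-up falling on those days is not taken as Day 14.
2. For PaO2/FiO2 and WHO, allow only post-baseline values to be carried to Day 7; otherwise leave Day 7 missing.
3. Set WHO to 10 at every scheduled time point after death.
4. Otherwise leave the Day 28 rule unchanged. A Day 25–31 window would exclude permitted follow-up at 14 ±3 days after the last dose: a last dose on Day 5 gives Days 16–22.
5. State whether section 8.4 or the actual study day governs early-discharge values.

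The cost is SAP wording and one derivation, with no new data. The drawback is that a few Day 7 values stay missing in the LOCF tables.
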